The central reader endoscopic score will be used for calculating the Endoscopic response for the evaluation of the efficacy endpoints. However, for stratification at the time of re-randomization, the endoscopic score at BL from central reader and the endoscopic score at Week 12 or Week 16 from site local reader will be used in order to determine response status.

Clinical response is defined as average daily liquid/soft stool frequency reduction of at least 30% from Baseline and average daily abdominal pain score not worse than Baseline OR average daily abdominal pain score reduction at least 30% from baseline and average daily stool frequency not worse than Baseline.

During this period of the study, subjects will visit the study site at Weeks 20, 28, 36, 44, and 52/Early Termination. A \pm 3-day window is permitted around scheduled study visits. The last dose of study drug is taken the evening prior to the Week 52 visit.

Subjects will be expected to remain on double-blinded therapy throughout the entire 36-week extension phase. However, subjects who are considered by the investigator to have not achieved meaningful symptomatic relief and meet the criteria for inadequate response at or after Week 20 will be eligible to receive the open-label therapy with ABT-494 12 mg BID, [Figure 2](#). Subjects who were re-randomized at Week 16 prior to Protocol Amendment 2 and are taking open-label ABT-494 24 mg QD will be transitioned to ABT-494 12 mg BID.

Subjects who still continue to meet criteria for inadequate response following a 4-week course of open-label ABT-494 12 mg BID will be eligible to dose escalate to open-label ABT-494 24 mg BID.

Subjects with persistent inadequate response while on ABT-494 12 mg BID or 24 mg BID may be withdrawn from the study at the investigator's discretion.

Criteria for Inadequate response are as follows:

- Average daily liquid/soft Stool Frequency > 2.2 OR average daily Abdominal Pain score > 1.8 AND
- An increase level of hs-CRP of at least 1 mg/L from Baseline or a hs-CRP ≥ 5 mg/L, either at the previous visit or at the current visit.

Note: hs-CRP will be performed by Central Lab. However, for the purpose of evaluating Inadequate Response criteria, hs-CRP can also be done at local lab.

Assessment of inadequate response should include consideration by the Investigator to rule out symptoms caused by reasons other than Crohn's disease related inflammation.

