5.0 Analysis Populations

5.1 Definition for Analysis Populations

The intent-to-treat responders (ITT-R) and intent-to-treat non-responders (ITT-NR) analysis sets includes all re-randomized subjects in the double-blind extension phase and are responders and non-responders at Week 16, respectively.

For the ITT-R and ITT-NR analysis sets, subjects are assigned to a treatment group based on the re-randomization schedule, regardless of the treatment actually received. The ITT-R and ITT-NR analysis sets will be used as primary sets for all efficacy analysis. Subjects who were randomized to placebo during the Induction Period will be summarized separately.

The intent-to-treat clinical responders (ITT-CR) and intent-to-treat clinical non-responders (ITT-CNR) analysis sets includes all re-randomized subjects in the double-blind extension phase and are clinical responders and clinical non-responders at Week 16, respectively.

For the ITT-CR and ITT-CNR analysis sets, subjects are assigned to a treatment group based on the re-randomization schedule, regardless of the treatment actually received. The ITT-CR and ITT-CNR analysis sets will be used for sensitivity analysis. Subjects who were randomized to placebo during the Induction Period will be summarized separately.

The safety analysis set consists of all subjects who received at least one dose of study medication in the Extension Phase. For the safety analysis sets, subjects are assigned to a treatment group based on the treatment actually received, regardless the treatment randomized. The safety analysis set will be used for all safety analysis of Extension phase.

Any ABT-494 analysis set will consist of all subjects who received at least one dose of ABT-494 during Induction or Extension. Any ABT-494 analysis set will be used for cumulative safety analysis (from Induction baseline to study end).

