| Week 12 (Week 28 of the study) | 85 | 2 – 169 |
| Week 36 (Week 52 of the study) | 253 | 170 – 999 |

Rx Day B = date of visit – date of first study drug in double-blind extension phase + 1

a. Day of first dose of study drug in double-blind extension phase.

CD-Related Corticosteroid Use

Subjects not on CD-related corticosteroids (systemic or rectal corticosteroids) at Induction Baseline which are then initiated during the study or who have dosages of these medications increased to greater than the dose taken at Baseline will be censored for efficacy assessments (i.e., will be considered non-responders for categorical endpoints and will have Baseline values carried forward for non-categorical assessments) from that point through the end of the study. These subjects will continue to be evaluated in the safety population.

The equivalent steroid dose will be determined based on the table below:

| Corticosteroid | Equivalent Dose (mg) |
|--------------------|----------------------|
| Cortisone | 25 |
| Hydrocortisone | 20 |
| Prednisone | 5 |
| Prednisolone | 5 |
| Triamcinolone | 4.0 |
| Methylprednisolone | 4.0 |
| Betamethasone | 0.75 |
| Dexamethasone | 0.75 |
| Budesonide | 1 |
| Beclomethasone | 5 |
| Beclometasone | 5 |

Open-Label Therapy

Subjects who are considered by the investigator to have not achieved meaningful symptomatic relief and have met the criteria for inadequate response at or after Week 20 of the study (Week 4 of the Extension Phase) will be eligible to receive open-label therapy with ABT-494 12 mg BID. These subjects will be censored for efficacy assessments (i.e., will be considered non-responders for categorical endpoints and will have the non-missing value prior to open-label therapy carried forward for non-categorical assessments) from that point through the end of the study.

Definition of Missing Data Imputation

The following imputation methods will be used to impute missing values in the efficacy analyses. In addition, an observed case analysis will be performed.

Non-Responder Imputation (NRI)

The NRI approach is used for binary efficacy variables. These variables can take values of 'Achieved' or 'Not Achieved' or may be missing for any reason including discontinuation from study. According to the NRI imputation approach, all missing values will be considered as 'Not Achieved.'

Last Observation Carried Forward (LOCF)

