For all variables (categorical variables and continuous variables), the following rules will be used for the LOCF approach:

1. Extension Baseline and Pre-Baseline values will not be used to impute the missing Post-Baseline values.
2. Missing values after Study Day 1 will be imputed using the latest non-missing values after Day 1 and prior to the missing value. If there are no non-missing values after Baseline, then the LOCF value will be missing.

Observed Case (OC)

Observed case analysis will be performed such that missing values will not be imputed. However, all observed values will be replaced by Induction Baseline value once subjects received CD-related corticosteroid therapy, or value prior to open label therapy once subjects moved to open-label therapy.

Mixed-Effect Model Repeated Measure (MMRM)

The MMRM model will be used for continuous efficacy variables with longitudinal data as the primary analysis. The MMRM model includes the baseline values as covariate, treatment, time point and treatment-by-time point interaction as fixed effects; and subjects within treatment as random effect. An unstructured (co)variance structure will be used to model the within-subject error. The comparison at a time point will be the contrast between treatments at that time point. Satterthwaite's approximation will be used to estimate denominator degrees of freedom.

Imputation of Missing Dates

For Baseline, efficacy, and safety parameters, if the day and/or month are missing, the following conventions will be used to impute the missing dates:

- 01 for missing start day

- End of month for missing end day
- January 1st for missing start month
- December 31st for missing end month

In case of partially missing AE start and stop dates, the dates will be imputed by comparing to first dose date of study medication so that the corresponding AEs will be made treatment-emergent whenever possible. If the start date of an AE is partially missing and the month is the same as the start date of a new therapy, the AE will be made treatment emergent to the new therapy.

In case of missing or partially missing study drug dosing dates, the dates will not be imputed. Subjects will be treated as not receiving dose on that date.

Rule for CDAI Calculation

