All colonoscopies shall be performed and recorded in video format. To be eligible for the study, the screening colonoscopy may be performed during the Screening Period (or up to 45 days before the Baseline visit if Amendment 2 is in place at the site). Colonoscopies will also be performed at the Week 12/16 visit and Week 52 visit. Investigators shall provide their SES-CD score assessment on the SES-CD score sheet for the baseline, Week 12/16 visit and Week 52 visit. The investigator SES-CD scores are to be entered in the appropriate eCRF, however neither the Investigator's Baseline, nor Week 12/16, Week 52 SES-CD scores will be used for the study's efficacy analyses unless the adjudicator agree with the site reading.

All videotaped colonoscopies will undergo central review. One primary central reviewer will evaluate the videotaped colonoscopies and provide the SES-CD scores to Parexel. A second central reviewer will adjudicate between the investigator's and the central reviewer's SES-CD scores if there is discrepancy (more than 10% difference) in total SES-CD score. The adjudicator will select the final SES-CD score that he/she most

agrees with from those provided by the investigator and the central reviewer, and this final SES-CD score will be entered into the study database and be used for the study's efficacy analyses. If there is no discrepancy between the investigator and the central reviewer, that central reviewer's score will be entered into the study database and serve as the SES-CD score to be used for the study's efficacy analyses.

If there is a missing SES-CD individual variable in the SES-CD score for the study's efficacy analyses (for all variables except the "Presence of Narrowing" variable), the following imputation rules will be applied:

If the same individual variable is:

- Missing at Week 52 but present at Week 12/16: the missing Week 52 value will be imputed based on the value at Week 12/16.
- Missing at Week 52 but no endoscopy performed at Week 12/16: the missing Week 52 value will be imputed based on the value at Induction Baseline.

If there is a missing SES-CD "Presence of Narrowing" individual variable in the SES-CD score for the study's efficacy analyses, the following imputation rules will be applied:

If the Presence of Narrowing individual variable is:

- Missing at Week 52 but present at Week 12/16: the missing Week 52 value will be imputed based on score at Week 12/16.

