Average daily stool frequency ≤ 1.5 and not worse than Induction baseline AND average daily abdominal pain ≤ 1.0 and not worse than Induction baseline.

Definition of Clinical Response

Average daily stool frequency at least 30% reduction from Induction baseline and average daily abdominal pain not worse than Induction baseline OR average daily abdominal pain at least 30% reduction from Induction baseline and average daily stool frequency not worse than Induction baseline.

Definition of Modified Clinical Remission

Average daily stool frequency ≤ 2.8 and not worse than Induction baseline AND average daily abdominal pain ≤ 1.0 and not worse than Induction baseline. This endpoint will only be analyzed among subjects with Induction baseline average daily stool frequency ≥ 4 or average daily abdominal pain ≥ 2.0 .

Definition of Enhanced Clinical Response

Average daily stool frequency at least 60% reduction from Induction baseline and average daily abdominal pain not worse than Induction baseline OR average daily abdominal pain at least 35% reduction from Induction baseline and average daily stool frequency not worse than Induction baseline or modified clinical remission.

Definition of Remission

Remission at Week 52 is defined as both Endoscopic remission at Week 52 AND Clinical remission at Week 52.

Definition of Response

Response at Week 52 is defined as both Endoscopic response at Week 52 AND Clinical response at Week 52.

EuroQol-5D-5L (EQ-5D)

EQ-5D is a standardized measure of health status developed by the EuroQol Group in order to provide a simple, generic measure of health for clinical and economic appraisal. The EQ-5D consists of 2 pages. The first page measures 5 dimensions of the health status (mobility, self-care, usual activities, pain/discomfort, and anxiety/depression) with 5 levels per dimension (no problems, slight problems, moderate problems, severe problems, and unable corresponding to Level 1 to Level 5 respectively). The second page is an EQ Visual Analogue Scale (EQ VAS). EQ-5D health states, defined by the EQ-5D-5L descriptive system on the first page, may be converted into a single index value. The change from baseline of the index value and EQ VAS will be analyzed and reported. UK scoring algorithm will be used ([Table 5](#)).

Table 5. An EQ-5D-5L Value Set for England

| | Central Estimate | Value for Health State 23245 |
|--|---|------------------------------|
| Mobility | | |
| No Problem | 0 | |
| Slight | 0.051 | 0.051 |

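### The Extension SAP's observed-case paragraph, read literally, gives subjects who switch to open-label drug their pre-switch value on categorical endpoints, in conflict with the SAP's own non-responder rule

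*SAP*

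**What the plan says.** Section 6.0 of the Extension SAP has two rules for a subject who goes to open-label therapy.

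- **Open-Label Therapy.** From the switch to the end of the study, such subjects "will be considered non-responders for categorical endpoints and will have the non-missing value prior to open-label therapy carried forward for non-categorical assessments". The two endpoint types are treated differently.
- **Observed Case (OC).** Missing values are not imputed, but observed ones are overridden after two events. For steroids the rule is that "all observed values will be replaced by Induction Baseline value once subjects received CD-related corticosteroid therapy". For a switch the same sentence names a different substitute: "or value prior to open label therapy once subjects moved to open-label therapy". The two endpoint types are not separated here.

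Section 5.1 defines ITT-R and ITT-NR as a pair that "includes all re-randomized subjects in the double-blind extension phase and are responders and non-responders at Week 16, respectively". Section 5.2 says that overall response needs both endoscopic and clinical response. It uses the central reader for efficacy endpoints, but the local Week 12 or 16 reading for response status at re-randomization. Section 5.1 does not say which reading decides ITT-R membership. On endoscopy timing, section 6.0 says: "Colonoscopies will also be performed at the Week 12/16 visit and Week 52 visit".

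**The concern.** Open-label therapy is offered for inadequate response, so a subject who takes it is a failure of the blinded dose. The Open-Label Therapy rule treats such subjects that way for categorical endpoints. The OC sentence, taken at its word, instead lets them keep whatever status they had before the switch. In ITT-R, that status comes from the endoscopy that helped qualify them for the set.

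The two halves of the OC sentence also pull in opposite directions. Substituting Induction Baseline after steroids means no change from baseline, hence failure on the response and remission endpoints. Substituting the pre-switch value after open-label therapy can mean success.

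At stake is a supporting table in which the arm with more rescue gains more apparent responders. Section 10.2 compares 3 mg BID with the higher doses, so a gap in rescue rates would feed directly into that contrast. By my count, 27 of the 32 extension endpoints in section 10.2 are proportions, so the categorical case is the common one.

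**Working it through.** The plan gives no figure on this point, so there is nothing to reproduce. I traced the rule and then sized it under stated assumptions.

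**1. Which SES-CD is carried.** A switch is possible from Week 20 (Extension SAP 6.0). Post-baseline endoscopy is scheduled only at Week 12/16 and Week 52 or early termination (6.0 and Table 1). The last scheduled SES-CD before a switch is therefore the Week 12/16 score. The LOCF rule in the same section bars carrying Extension Baseline values forward; literal OC carries exactly such a value.

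**2. One subject.** Endoscopic response is a reduction of at least 25% from Induction Baseline. Take Induction Baseline 12, Week 12/16 score 9, observed Week 52 score 14, with a switch in between.
- Literal OC: (12 − 9)/12 = 25.0%, responder.
- Open-Label Therapy rule: non-responder.
- Observed Week 52 score: worse than baseline, non-responder.
- Steroid branch, if it applied: (12 − 12)/12 = 0%, non-responder.

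Endoscopic remission, endoscopic healing or SES-CD ≤ 2 reached at Week 12/16 would be carried in the same way.

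**3. Clinical endpoints.** The symptom part of inadequate response is "Average daily liquid/soft Stool Frequency > 2.2 OR average daily Abdominal Pain score > 1.8 AND" an hs-CRP condition (a rise of at least 1 mg/L, or a level of at least 5 mg/L). The investigator must also judge that meaningful relief was not achieved. Given that judgement:
- Stool frequency (SF) falling from 6 to 3, abdominal pain (AP) not worse than baseline, and hs-CRP 6 meets the criteria and is also clinical response (50% reduction).
- SF falling from 5 to 2.5, AP 0.9 and not worse than baseline, and hs-CRP 6 meets the criteria and is also modified clinical remission (SF ≤ 2.8, AP ≤ 1.0, baseline SF ≥ 4).
- Clinical remission (SF ≤ 1.5 and AP ≤ 1.0) cannot coincide with SF > 2.2 or AP > 1.8. If the qualifying scores are the carried value, neither clinical remission nor composite remission is falsely credited.

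**4. Size for endoscopic response in ITT-R.** Let r be the share of an arm that switches, q the response rate among the rest, and f the share of switched ITT-R subjects who miss 25% on the analysis score. With everyone scoped at Week 52:
- switched subjects as failures: (1 − r)q
- literal OC: (1 − r)q + r(1 − f)

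The difference is r(1 − f) per arm. With f equal in both arms, the 12 mg minus 3 mg contrast moves by −(r3 − r12)(1 − f), whatever q is. If q is also equal, the literal OC contrast is −(r3 − r12)(1 − f − q), which is negative only when q < 1 − f.

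The documents give no rescue rates, so all inputs below are assumptions.

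| r: 3 mg / 12 mg | q: 3 mg / 12 mg | f | Switched = failure | Literal OC | Shift |
|---|---|---|---|---|---|
| 40% / 15% | 60% / 60% | 0 | 36.0% v 51.0% (+15.0) | 76.0% v 66.0% (−10.0) | −25 |
| 40% / 15% | 60% / 60% | 20% | 36.0% v 51.0% (+15.0) | 68.0% v 63.0% (−5.0) | −20 |
| 40% / 15% | 80% / 80% | 20% | 48.0% v 68.0% (+20.0) | 80.0% v 80.0% (0) | −20 |
| 40% / 20% | 50% / 70% | 0 | 30% v 56% (+26) | 70% v 76% (+6) | −20 |

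**5. Incomplete endoscopy.** Take r = 40% / 20%, q = 60%, f = 0, with 90% of non-switchers and 70% of switchers scoped. The denominators are 0.6 × 0.9 + 0.4 × 0.7 = 0.82 and 0.8 × 0.9 + 0.2 × 0.7 = 0.86.
- Failures: 0.324/0.82 = 40% v 0.432/0.86 = 50%.
- Literal OC: 0.604/0.82 = 74% v 0.572/0.86 = 67%.

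**The case against.** The best defence is that the Open-Label Therapy rule stands apart from the imputation methods and runs to the end of the study. It can be read as governing every analysis, with the OC sentence restating only the value-replacement half. The Induction SAP uses the same shorthand: its steroid rule separates the endpoint types and its OC sentence does not. This is a fair reading and may be what was meant. But the shorthand is harmless in the Induction SAP, because Baseline is the only substituted value and gives failure. The Extension SAP adds a different substitute, and that protection is lost.

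Three stronger conclusions that a reader might draw are not supported.

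- *Every switched ITT-R subject with a Week 52 endoscopy becomes a responder.* Section 5.1 does not name the reading behind ITT-R. If membership follows the local reading used at re-randomization, some members will miss 25% on the central or adjudicated score. The OC sentence also sets no order between the steroid and open-label branches, so a subject meeting both could receive Induction Baseline and fail.
- *The OC analysis is the designated check on NRI.* Section 10.2 names LOCF as the sensitivity analysis; OC is an additional analysis announced in section 6.0. Extension endpoints have no multiplicity control (section 10.3).
- *The dose contrast reverses.* Reversal in an equal-q grid follows from the formula whenever q < 1 − f and is not independent evidence. With 50% v 70% among non-switchers the literal OC contrast is still +6.

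**Conclusion.** The OC paragraph is wrong as written: it conflicts with the Open-Label Therapy rule for categorical endpoints. Under the literal reading, a switched ITT-R subject with a Week 52 endoscopy counts as an endoscopic responder if ITT-R status rests on the central or adjudicated score and the steroid branch does not apply. Clinical response and modified clinical remission can be affected too. Clinical remission cannot, when the scores that qualified the subject for rescue are the ones carried.

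With all subjects scoped and f equal in both arms, the bias favours the arm with more rescue by (difference in rescue rates) × (1 − f). That is 20 to 25 points for an assumed 25-point rescue gap and f from 20% to 0. The contrast between 3 mg BID and a higher dose may shrink, vanish or reverse, depending on rates that the documents do not give. The problem is confined to the additional OC analysis. Under NRI with the Open-Label Therapy rule, switched subjects are already non-responders.

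**What to change.** Amend the OC paragraph of the Extension SAP along these lines: after a switch to open-label therapy, or after the steroid event defined under CD-Related Corticosteroid Use, categorical endpoints are Not Achieved; replacement by the pre-switch or Induction Baseline value applies to non-categorical endpoints only. Both branches then give the same categorical result, so their order no longer matters for those endpoints. It would also help to name in section 5.1 the SES-CD reading that defines ITT-R and ITT-NR.

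The cost is a short SAP edit, with no new data and no change to trial conduct. Compared with the literal reading, OC response rates will be the same or lower, and they will agree with the main rule.

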4.2 Design Diagram

[figure not shown]
This is a Phase 2, multicenter, randomized, double-blind, placebo-controlled study designed to evaluate the efficacy, safety, and pharmacokinetics of ABT-494 as induction

therapy in subjects with moderately to severely active Crohn's disease and evidence of mucosal inflammation defined by a SES-CD ≥ 6 (or ≥ 4 for subjects with disease limited to the ileum) and average daily soft/liquid stool frequency ≥ 2.5 or average daily abdominal pain score of ≥ 2.0 ; and CDAI ≥ 220 and ≤ 450 , with a history of inadequate response or intolerance to immunomodulators and/or anti-TNF therapy. The study will allow enrollment of up to 30% of subjects who were primary non responders to anti-TNF treatment.

The study is designed to enroll approximately 210 subjects to meet scientific and regulatory objectives without enrolling an undue number of subjects in alignment with ethical considerations. Therefore, if the target numbers of subjects have been enrolled, there is a possibility that additional subjects in screening will not be enrolled.

The study duration could be up to 60 weeks, including a Screening Period of up to 35 days, a 16-week double-blind induction period, a 36-week double-blind extension phase, and a 30-day follow-up period. Subjects who met eligibility criteria were randomized in a 1:1:1:1:1:1 ratio to one of the double-blinded induction treatment arms.

[figure not shown]
The schematics of the overall study design are shown in [Figure 1](#) and [Figure 2](#).

Figure 1. Study Design Schematic

*The 6 mg BID dose arm was added to replace the 24 mg QD dose arm in Protocol Amendment 2

**Subjects who were re-randomized at Week 16 to 24 mg QD prior to Protocol Amendment 2 will continue to receive the double-blind 24 mg QD dose until Week 52/PD.

Figure 2. Study Design Schematic for Open-Label Extension Option for Patients Who Do Not Adequately Respond During the Extension Phase

Screening Period

Within 35 days prior to the Baseline Visit, subjects received a full explanation of the study design and study procedures, provided a written informed consent, and underwent the screening procedures as outlined in [Table 1](#).

An e-diary was dispensed and training were provided to the subject at the Screening Visit.

Laboratory tests performed during the Screening period can be repeated in case the abnormalities are considered to be transient by the investigator.

16-Week Induction Period

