10.2 Efficacy Analyses

The endpoints (Double-Blind Extension Phase) include:

- Proportion of subject who achieve remission at Week 52.
- Proportion of subjects who achieve endoscopic remission at Week 52.
- Proportion of subjects who achieve both endoscopic remission and modified clinical remission at Week 52.
- Proportion of subjects who achieve clinical remission over time.
- Proportion of subjects who maintain clinical remission over time among subjects in clinical remission at Week 16.
- Proportion of subjects who achieve modified clinical remission over time.
- Proportion of subjects who maintain modified clinical remission over time among subjects in modified clinical remission at Week 16.
- Proportion of subject who achieve response at Week 52.
- Proportion of subjects with SES-CD ≤ 2 at Week 52.

- Proportion of subjects with SES-CD = 0 at Week 52.
- Proportion of subjects who achieve endoscopic response at Week 52.
- Proportion of subjects who achieve enhanced endoscopic response at Week 52.
- Proportion of subjects who achieve endoscopic improvement at Week 52.
- Proportion of subjects who achieve endoscopic healing at Week 52.
- Proportion of subjects who achieve clinical response over time.
- Proportion of subjects who achieve enhanced clinical response over time.
- Proportion of subjects who maintain enhanced clinical response over time among subjects in enhanced clinical response at Week 16.
- Proportion of subjects with an average daily SF ≥ 2.5 AND average daily AP ≥ 2.0 at Induction Baseline who achieve clinical remission over time.
- Proportion of subjects taking corticosteroids at Induction Baseline who discontinued corticosteroid use and achieved CDAI < 150 over time.
- Proportion of subjects taking corticosteroids at Induction Baseline who discontinued corticosteroid use and achieve remission at Week 52.
- Proportion of subjects taking corticosteroids at Induction Baseline who discontinued corticosteroid use and achieve clinical remission over time.
- Proportion of subjects taking corticosteroids at Induction Baseline who discontinued corticosteroid use and achieve modified clinical remission over time.
- Proportion of subjects taking corticosteroids at Induction Baseline who discontinued corticosteroid use and achieve endoscopic remission at Week 52.
- Proportion of subjects who achieve CDAI < 150 at over time.
- Proportion of subjects with decrease in CDAI ≥ 70 points from Induction Baseline over time.

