12.0 Summary of Changes

12.1 Summary of Changes Between the Latest Version of Protocol and the Current SAP

The following efficacy variables are not mentioned in the protocol:

Modified Clinical Remission: Average daily stool frequency \leq 2.8 and not worse than baseline AND average daily abdominal pain \leq 1.0 and not worse than Induction baseline. This endpoint will only be analyzed among subjects with baseline average daily stool frequency \geq 4 or average daily abdominal pain \geq 2.0.

Enhanced Clinical Response: Average daily stool frequency at least 60% reduction from baseline and average daily abdominal pain not worse than baseline OR average daily abdominal pain at least 35% reduction from baseline and average daily stool frequency not worse than baseline.

Enhanced Endoscopic Response: SES-CD reduction from Induction baseline > 50% (or for a Baseline SES-CD of 4, at least a 2 point reduction from Baseline).

Endoscopic Improvement: SES-CD reduction from Induction baseline > 50% or endoscopic remission.

Endoscopic Healing: SES-CD ulcerated surface subscore of 0 in subjects with SES-CD ulcerated surface subscore ≥ 1 at Induction Baseline.

SES-CD ≤ 2

SES-CD = 0

12.2 Summary of Changes Between the Previous Version and the Current Version of the SAP

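### The Extension SAP defines enhanced clinical response in two ways, and does not say whether the baseline limit on modified clinical remission applies inside it

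*SAP*

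**What the plan says.** The Extension SAP adds enhanced clinical response to the protocol's endpoints and states it in two places.

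- **Section 6.0, Analysis Conventions.** A subject qualifies with a 60% SF reduction and AP not worse, or a 35% AP reduction and SF not worse. The sentence then closes with "average daily stool frequency not worse than Induction baseline or modified clinical remission".
- **Section 12.1, variables not in the protocol.** The same two rules appear, ending at "average daily abdominal pain at least 35% reduction from baseline and average daily stool frequency not worse than baseline". Modified clinical remission is not mentioned.

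Section 6.0 defines modified clinical remission as "Average daily stool frequency ≤ 2.8 and not worse than Induction baseline AND average daily abdominal pain ≤ 1.0", with AP also not worse than Induction baseline. No minimum reduction is required. It then adds: "This endpoint will only be analyzed among subjects with Induction baseline average daily stool frequency ≥ 4 or average daily abdominal pain ≥ 2.0".

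Two endpoints in Section 10.2 use enhanced clinical response: "Proportion of subjects who achieve enhanced clinical response over time" and "Proportion of subjects who maintain enhanced clinical response over time among subjects in enhanced clinical response at Week 16". Neither states a baseline limit. The symptom entry criterion in Section 4.2 is "average daily soft/liquid stool frequency ≥ 2.5 or average daily abdominal pain score of ≥ 2.0", together with CDAI 220 to 450.

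**The concern.** There are two separate gaps. First, the sections give different rules, so a subject's responder status can depend on which one is programmed. For the maintenance endpoint this also changes the denominator, because that set is defined by enhanced response at Week 16.

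Second, modified clinical remission is a threshold and not a reduction. Its baseline limit is what makes reaching the threshold amount to improvement. The limit is worded as a restriction on who is analysed for that one endpoint, and nothing says it travels with the term when the term is reused. Without it, an endpoint named as stricter than clinical response can be met by a subject who fails clinical response, which needs a 30% reduction.

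**Working it through.** The plan attaches no figure to this endpoint, so there is nothing to reproduce. The check works from the definitions. Write SF0 and AP0 for the Induction baseline averages, and SF and AP for follow-up.

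**Step 1. Where the two sections disagree, taking the clause as a third limb.** A subject counts under Section 6.0 but not under Section 12.1 when all of these hold:

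- modified remission is met: SF ≤ 2.8, AP ≤ 1.0, neither worse than baseline;
- the SF limb is missed: SF > 0.40 × SF0, so SF0 < 2.8 / 0.40 = 7.0;
- the AP limb is missed: AP > 0.65 × AP0, so AP0 < 1.0 / 0.65 = 1.54 (or AP0 = 0, where no percentage reduction is possible).

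Since AP0 is below 2.0, such a subject can have entered only on SF ≥ 2.5. The range is therefore SF0 from 2.5 to just under 7.0. If the baseline limit carries over, it must be met through SF, and the range is 4 to just under 7.0.

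These subjects are not all non-improvers. With AP steady at 1.0, SF from 6.0 to 2.714 (19 stools in 7 days) is a reduction of 1 − 2.714/6.0 = 54.8%. It counts under Section 6.0 and not under Section 12.1.

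**Step 2. Unchanged subjects, with no baseline limit.** Setting SF = SF0 and AP = AP0, modified remission needs SF0 ≤ 2.8 and AP0 ≤ 1.0, and entry needs SF0 ≥ 2.5. The attainable diary averages are:

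| Diary days | SF values | AP values from 0 to 1.0 | Baseline combinations |
|---|---|---|---|
| 4 | 2.5, 2.75 | 5 | 10 |
| 5 | 2.6, 2.8 | 6 | 12 |
| 6 | 2.5, 2.667 | 7 | 14 |
| 7 | 2.571, 2.714 | 8 | 16 |

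Under Section 12.1 the count is 0 in every row. These are possible score combinations, not numbers of subjects.

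**Step 3. Can such a subject be eligible on CDAI?** Yes, with assumed values for the other items: SF sum 18 × 2 = 36, AP sum 7 × 5 = 35, well-being sum 14 × 7 = 98, one listed category × 20 = 20, male hematocrit 41 giving (47 − 41) × 6 = 36. The total is 225, against a minimum of 220.

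**Step 4. Enhanced responders who are not clinical responders, with no baseline limit.** Both reductions must be under 30%, so SF0 < 2.8 / 0.70 = 4.0 and AP0 < 1.0 / 0.70 = 1.43. The unchanged subjects of step 2 are the extreme case.

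**Step 5. The same check with the baseline limit applied.** A modified remitter with SF0 ≥ 4 has an SF reduction of at least 1 − 2.8/4 = 30%. One with AP0 ≥ 2.0 has an AP reduction of at least 1 − 1.0/2.0 = 50%. Either meets clinical response, so the step 4 group is empty. Subjects with AP0 ≥ 2.0 already pass the 35% limb, so the clause then adds only subjects with SF0 from 4 to just under 7.0.

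**Step 6. The other way to parse the sentence.** If the clause is an alternative only to the SF-not-worse condition inside the AP limb, it has no effect, because modified remission already requires SF not worse. Section 6.0 then gives the same result as Section 12.1 for every combination.

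**The case against.** Section 6.0 holds the operative conventions, and Section 12.1 is a short list that also abbreviates Induction baseline to baseline. A programmer would probably work from Section 6.0. That is fair, but neither section is said to prevail. Section 12.1 does not describe superseded wording: it lists current additions in the first Extension SAP, and its other definitions agree in substance with Section 6.0.

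A reader might infer that Section 6.0 plainly lets subjects with no improvement count. The documents do not support that as a flat statement. It needs the third-limb parsing and also needs the baseline limit to be dropped. The limit sits under the heading that defines modified clinical remission, and the Induction SAP applies it each time it uses the term, so carrying it over is a reasonable reading. What remains is that the limit governs analysis of a different endpoint, and enhanced clinical response states none. The parsing that makes the clause harmless also makes it redundant, so a third limb is the more natural intention.

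The unchanged-score group is also narrow. At SF 2.714 and AP 1.0 the diary items give 19 × 2 + 7 × 5 = 73 CDAI points, leaving at least 147 to come from other items. Such a subject exceeds the SF > 2.2 symptom threshold for inadequate response, and after a move to open-label therapy would be set to non-responder. That covers only those who also meet the hs-CRP condition, are judged by the investigator to lack meaningful relief, and actually switch.

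**Conclusion.** The mismatch between Sections 6.0 and 12.1 is real on the face of the text. It affects classification if the clause is a third limb, over baseline SF 2.5 to just under 7.0 (4 to just under 7.0 with the limit) and AP below about 1.54. Counting unchanged subjects is a conditional consequence, confined to SF 2.5 to 2.8 with AP 1.0 or lower.

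The documents do not give the number of subjects in either range, so no effect on response rates can be computed, and it is not established that two analysts would in fact report different counts. For scale only: with no dropout, 5 × 35 = 175 active-induction subjects over three extension doses is about 58 per arm. One reclassified subject would move an arm's rate by about 1/58 = 1.7 percentage points, and by more once responders and non-responders are analysed separately.

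Two of the 32 endpoints in Section 10.2 are touched, without multiplicity control. The co-primary endpoints, sample size and significance level are not. This is a minor drafting correction.

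**What to change.** Put one definition in both Section 6.0 and Section 12.1. Either drop the modified-remission clause, or write it as a numbered third limb that counts only for subjects with Induction baseline SF ≥ 4 or AP ≥ 2.0. All other subjects stay in the denominator and are judged on the 60% and 35% limbs. With either choice, every enhanced responder is also a clinical responder. The cost is about one sentence in each section and no new data. It should be settled before the extension data are analysed.
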